ASD Parent Trainer: Online Coaching for Parents of Children With Autism NCT02469870

Study Protocol and Analysis Plan

3/2/17

Study Protocol and Analysis Plan

We employed a mixed-model repeated measures, randomized group design to evaluate the PR and TR programs, examining changes over time both within and across the programs, assessing whether there were improvements in each program. All research was conducted online. Participants were recruited nationally. Eligible parents had to (a) have access to necessary technology (i.e., computer with camera and microphone, high-speed Internet connection, and a mobile device with current operating system) and (b) speak English. Parents had to have at least one child who (a) had a medical diagnosis or special educational eligibility of ASD, (b) was between 3 – 8 years old, (c) lived in the home of the participating parent, and (d) engaged in challenging behavior that interfered with at least one family routine. Eligible participants completed informed consent online. Parents were assigned to either the PR or TR condition using block randomization.

Measures

To evaluate changes over time both within and between programs, we assessed family quality of life; parenting stress, behaviors, and knowledge; and child behavior (adaptive and maladaptive) using parent report measures. Additionally, at T3 we examined parents use of and satisfaction with the programs. The measures described in the following sections were used.

Quality of Life. The Family Quality of Life survey (FQOL; Summers et al., 2005) is a 25-item measure for families raising a child with intellectual or developmental disabilities. The measure includes domains of parenting, emotional well-being, physical/material well-being, and disability-related supports using a 5-point scale with responses ranging from (1) very dissatisfied to (5) very satisfied. In the current study we used the mean FQOL scores for analyses, which demonstrated excellent internal reliability (alpha = .91 at pretest).

Parenting Stress. The Parental Stress Scale (PSS; Berry & Jones, 1995) was developed to assess stress of parenting stress, and contains 18 items representing both positive and negative parenthood components. In the current study, it demonstrated strong internal reliability (alpha = .90 at all three time points), so all analyses used parents' mean scores.

Parenting Practices. The Parenting Scale (PS; Arnold, O'Leary, Wolff, & Acker, 1993) and the Bangor Mindful Parenting Scale (BMPS; Jones et al., 2014) were administered. The PS is a 30-item scale with three subscales (laxness, over-reactivity, and hostility). The BMPS is a 15-item instrument designed to measure parental mindfulness measuring five domains: observing, describing, acting with awareness, nonreactivity, and nonjudgement. For the current study, we used the overall mean for the PS (alpha = .77 at pretest) and total mindful parenting score on the BMPS (alpha = .85 at pretest). To measure parental knowledge, we developed a 20-item multiple choice/true-false test (alpha = .47 at pretest). The test included items related to principles of ABA and routine-based intervention strategies, as well as five questions on mindfulness practice because that content was included in the PR program.

Child Behavior. This was measured with the Strengths and Difficulties Questionnaire– Parent Report (SDQ-P; Goodman, 1997) and the Scales of Independent Behavior-Revised (SIB-R; Bruininks, Woodcock, Weatherman, & Hill, 1996). The SDQ is a 25-item parent-report version of a behavioral screening questionnaire. It assesses both positive and negative behaviors in the following domains: conduct problems, inattention-hyperactivity, emotional symptoms, peer problems, and pro-social behavior. The SBI-R is a 40-item scale that measures 14 areas of adaptive behaviors and 8 areas of maladaptive behaviors. The current study analyzed means of the total difficulty scale (alpha = .80 at pretest) and the adaptive (alpha = .92 at pretest) and maladaptive behaviors (alpha = .90 at pretest) subscales of the SIB-R, as well as the internalizing and externalizing subscale of the SDQ.

Consumer satisfaction was evaluated using a 9-item, 6-point Likert scale asking about the participants' use and satisfaction with the programs. The consumer satisfaction items were combined into a single measure with strong internal reliability (alpha = .93). Responses to open-ended questions in the consumer satisfaction instrument were subjected to a thematic analysis by two separate reviewers. The responses were analyzed by compiling topics and identifying emergent themes using inductive content analysis. Two authors worked independently to develop core themes and then met to review their lists. Conflicts were discussed until consensus was reached.

Participants were sent T1 approximately one week prior to accessing the Learning Management System (LMS), which housed both programs. Parents were notified to which group they were randomly assigned upon completion of T1. Participants were sent T2 six weeks after T1, and T3 was sent 4 weeks later. Honorarium checks in the amount of \$50 were mailed within four weeks of each survey completion. Participants who did not attend any PR sessions were not sent T2 or T3.

Program Descriptions

Both programs focused on ABA within the context of typical family routines. The content guided parents to identify target routines and behaviors of concern, learn about the patterns that may be affecting their children's behavior, and develop strategies to prevent problems, teach skills, and manage access to reinforcement. The LMS courses were divided into modules that included videos, written summaries of each video, fillable forms and other exercises to guide parents through activities to support the intervention process with their

children, and resource materials including links to relevant websites. The parents were expected to complete homework for each module. Parents were given access to the courses for the duration of the study and technical support was available.

Teaching Routines. Teaching Routines was entirely self-directed. The program included eight modules with videos for each ranging 3 – 5 minutes in duration. The topics were antecedent-behavior-consequence method, creating task analyses, antecedent-based strategies, communication, reinforcement, teaching methods, and overcoming obstacles. Participants were assigned six activities using fillable forms and provided additional resources including examples, a glossary of terms, and a list of websites. No feedback was given to the parents apart from the automated completion responses. The participants were given access to the TR LMS for the duration of the study, but post and follow-up assessments were completed at 6 and 10 weeks (i.e., same as the PR condition).

Practiced Routines. Practiced Routines was a facilitated program. It was organized into four modules that included a total of seven videos ranging from 3-13 minutes each. The topics overlapped with those in the TR program, but included more explicit information on function-based strategies, as well as mindfulness practice. Participants were assigned six fillable forms, and provided supplemental data collection tools. Additional resources focused on mindfulness and PBS within family routines. Eighteen brief guided audio meditations were available to participants via the Practiced Mind[™] mobile application. The meditations focused on bringing the parents' awareness to both internal and external experiences and helping them act intentionally.

When participants were assigned to PR, they were grouped based on their availability and assigned to one of five parent educators. Parents were encouraged to attend a brief "tech check"

(via WebEx) to test their computer (e.g., webcam, video) and Internet connection. The parent educators contacted participants prior to and between three weekly online meetings via email or phone, not exceeding a total of 10 minutes per participant to check on their progress and respond to questions. The online meetings were held using WebEx video conferencing software with small groups of parents (M = 3.7; range = 1 – 5) per cohort. They lasted between 1.5 and 2 hours, with most approaching 2 hours. Meetings were organized using PowerPointTM presentations and session guides. A technology support specialist was available during the meetings for assistance.

Treatment Integrity. Because TR was self-directed, it was not necessary to evaluate treatment integrity beyond ensuring that the participants were able to log on to the platform and access all resources consistently. Specific provisions, however, were implemented in PR to ensure that the parent educators were consistent in delivery. Parent educators were master's and doctoral level professionals experience in behavioral intervention with children with ASD and their families. They were provided with training that involved selected readings on positive behavior support and mindfulness, review of the LMS resources, and instruction on facilitating the sessions and using the online meeting system and LMS.

Fidelity checks were conducted for 34% of the sessions. The fidelity checklist included items on content and parent participation. Fidelity for content ranged from 90-100% (M = 99%). Fidelity for participation ranged from 53-100% (M = 94%). Interrater reliability was conducted for 38% of sessions assessed by a second observer. Reliability was evaluated on an item-by-item basis, dividing the number of agreements by agreements plus disagreements and multiplying by 100 to obtain a percentage. Reliability was 87.5% for the content and 97.5% for participation. Dosage was measured as the percent of components (e.g., videos, forms, supplemental resources) accessed by the participants.

Data Analysis

Change was evaluated over time within condition using repeated-measures *t*-tests. To address hypotheses predicting differential change in outcome measures between condition over time we used analysis of covariance (ANCOVA) models that allow for examination of crosssectional effects and mean adjusted outcomes. The ANCOVA models (adjusted for baseline scores) were used for analyses of change in the outcome measures at posttest and follow-up.

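### PR parents who attended no session were not sent the T2 and T3 surveys, so if there were any, the between-arm ANCOVA is not a comparison as randomised

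*Combined protocol and SAP*

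**What the plan says.** The opening section describes a randomised comparison: "Parents were assigned to either the PR or TR condition using block randomization". The assessment schedule at the end of Measures then fixes the order of events: "Parents were notified to which group they were randomly assigned upon completion of T1". T2 follows T1 by six weeks and T3 comes four weeks after T2. The same paragraph adds: "Participants who did not attend any PR sessions were not sent T2 or T3".

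Program Descriptions says that TR was self-directed throughout and that its post and follow-up assessments took place at 6 and 10 weeks, as in PR. No minimum use is stated as a condition for sending them. The only check described for TR, under Treatment Integrity, is "ensuring that the participants were able to log on to the platform and access all resources consistently", and it is not tied to T2 or T3. In PR, parents had to join three weekly group meetings, for which "they were grouped based on their availability and assigned to one of five parent educators".

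Data Analysis specifies repeated-measures t-tests within condition and, between conditions, ANCOVA adjusted for baseline at posttest and follow-up. It names no analysis set, intention-to-treat rule, missing-data method or sensitivity analysis.

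**The concern.** The rule makes outcome collection in one arm depend on what parents did after randomisation. It is not ordinary dropout: the outcomes were never requested. A TR parent with the same time pressure, motivation or home situation was still surveyed. Read literally, the sentence would also exclude every TR parent, since none attended a PR session; but TR assessments were completed, so the rule can operate only in PR.

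If it excluded anyone, each T2 and T3 between-arm result compares PR attenders with TR parents who replied. Attenders and non-attenders may differ in ways that the T1 score does not capture, and that part of the difference enters the estimated PR effect. Nor can PR non-attenders be set aside as untreated. The text says "Parents were given access to the courses for the duration of the study and technical support was available", and outside the meetings "Eighteen brief guided audio meditations were available to participants via the Practiced Mind" mobile application. Even a wholly untreated parent belongs in a comparison as randomised.

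At stake is whether the between-arm results can be read as randomised evidence. The data in hand cannot show that the selection was harmless, because the outcomes needed to check it do not exist.

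**Working it through.** **No figure to reproduce.** The documents give no sample size, power calculation, dropout rate or count of PR non-attenders. Every input below is an assumption.

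**Inputs.** All effects are in residual SD, meaning the SD of the outcome given T1. If T1 and outcome correlate 0.6, one residual SD is √(1 − 0.36) = 0.8 raw SD.
- n: parents randomised per arm, 60 unless stated
- q: share of parents who would attend no PR session, equal in both arms by randomisation
- d: how much worse such parents do than attenders with the same T1 score
- s: share of their TR counterparts who do not return the survey
- no true effect; two-sided 5% test

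**Formulas.** PR contains only attenders. Among TR responders, a fraction q(1 − s)/(1 − qs) are of the non-attender type. Hence:
- bias = d·q(1 − s)/(1 − qs)
- SE = √[1/(n(1 − q)) + 1/(n(1 − qs))]
- rejection = Φ(−1.96 + bias/SE) + Φ(−1.96 − bias/SE)

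**Worked case.** With n = 60, q = 0.2, d = 0.5, s = 0: bias = 0.5 × 0.2 = 0.10; SE = √(1/48 + 1/60) = 0.194; bias/SE = 0.516; rejection = Φ(−1.444) + Φ(−2.476) = 8.1%.

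**Bias and rejection rate, n = 60, d = 0.5:**

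| q | s = 0 | s = 25% | s = 50% | s = 75% | s = 100% |
|---|---|---|---|---|---|
| 0 | 0; 5.0% | 0; 5.0% | 0; 5.0% | 0; 5.0% | 0; 5.0% |
| 10% | 0.050; 5.8% | 0.038; 5.5% | 0.026; 5.2% | 0.014; 5.1% | 0; 5.0% |
| 20% | 0.100; 8.1% | 0.079; 6.9% | 0.056; 5.9% | 0.029; 5.2% | 0; 5.0% |
| 30% | 0.150; 11.6% | 0.122; 9.1% | 0.088; 7.1% | 0.048; 5.6% | 0; 5.0% |

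With d = 0.2 and s = 0, the values are 0.04 and 5.5% (q = 20%), and 0.06 and 6.0% (q = 30%). If non-attenders do better than T1 predicts, d changes sign: the bias then works against PR and the rejection rates are unchanged.

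**Simulation check.** In 10,000 trials with n = 60, T1–outcome correlation 0.6 and d = 0.5, ANCOVA bias at s = 0 was 0.099 (q = 20%) and 0.150 (q = 30%), with rejection 7.7% and 11.3%. At s = 50% the biases were 0.057 and 0.088, with rejection 6.3% and 6.5%. Imputing T2/T3 by arm from T1 gave the same bias as ANCOVA in all four cases, so it does not repair the problem. Shifting imputed PR values by −0.5 removed the bias at s = 0 but over-corrected at s = 50% (−0.043 and −0.062). Shifting both arms left 0.007 and 0.013.

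**Tipping point.** Suppose the ANCOVA shows a PR advantage E = 0.50 residual SD (0.40 raw), with n = 60 and s = 0. Restoring non-attenders who do δ worse than T1 predicts lowers the estimate by qδ. Holding SE fixed, significance is lost at δ = (E − 1.96·SE)/q:
- q = 10%: (0.500 − 0.368)/0.1 = 1.32 (1.06 raw)
- q = 20%: (0.500 − 0.380)/0.2 = 0.60 (0.48 raw)
- q = 30%: (0.500 − 0.394)/0.3 = 0.35 (0.28 raw)

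**The case against.** The strongest reply is that harm is not shown. The documents give no q, no N and no direction, and with q = 0 the rule did nothing. That is right about size and is why the conclusion is conditional. It does not remove the defect: the rule is written into the plan, and a reader cannot tell from the documents whether it excluded anyone.

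The plan also never calls its ANCOVA intention-to-treat, and its aims include improvement within each program, so a comparison of attenders could have been intended. If so, the plan needed to say so. A contrast filtered by attendance in one arm only is still not a like-for-like comparison.

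The opening section does say "We employed a mixed-model repeated measures, randomized group design to evaluate the PR and TR programs". But the between-arm analysis actually specified is ANCOVA, and a likelihood-based mixed model keeping T1-only parents would itself assume that their outcomes are missing at random.

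Four smaller points stand. Most illustrative scenarios keep rejection below 7%, and values above 9% need q = 30% with s of 25% or less. Tipping values depend heavily on how close the assumed result already is to p = 0.05: at 40 per arm the margin E − 1.96·SE is only 0.050, 0.035 and 0.017 for q = 10%, 20% and 30%. Grouping by availability may have eased attendance, so scheduling as a cause of non-attendance is inference. Finally, the document is in the past tense and reports reliability at all three time points, so a new survey at 6 and 10 weeks is probably too late for this trial.

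**Conclusion.** The concern holds, with high confidence as to the rule and the undefined analysis set. The plan withholds outcome assessment on a post-randomisation event that can occur only in PR, and the stated ANCOVA cannot restore the randomised comparison. If any PR parent attended no session, the T2 and T3 between-arm results are a non-intention-to-treat contrast that is not labelled as one. This must be fixed.

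The size and direction of any bias cannot be obtained from the documents. Under the assumptions above, the effect runs from none (q = 0, or no TR counterpart replies) to material (0.15 residual SD and 11.6% rejection at q = 30%, d = 0.5, s = 0). The severity rests on the rule and on the unlabelled contrast, not on these illustrative figures.

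**What to change.** With the existing data:
1. Report by arm the numbers randomised, sent and returning T1, T2 and T3, with the T1 profile and any logged use of course components for PR non-attenders. If there were none, say so and the matter closes.
2. Otherwise, label the ANCOVA as a non-intention-to-treat comparison restricted to attenders in PR.
3. Add a tipping-point analysis over all randomised parents. Impute missing T2 and T3 by arm from the T1 measures, stating that this step alone makes nearly the same assumption as the ANCOVA. Then shift the imputed values in both directions, in labelled residual SD, until the conclusion changes or the shift becomes implausible. Vary the shift separately for PR non-attenders and TR non-responders. A range of −0.5 to +0.5 may be too narrow, since the q = 20% example tips at 0.60.

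The cost is one flow and T1 table, one relabelled analysis and one sensitivity analysis.

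If surveys can still be sent, or in a future trial, delete the rule, send T2 and T3 to every randomised parent at 6 and 10 weeks, and analyse as randomised. That costs two online surveys and 2 × $50 = $100 in honoraria per PR non-attender. It removes the bias due to the rule but not that from ordinary non-response. For example, with d = 0.5, if non-attender-type parents reply at 25% in PR and 50% in TR, the bias is 0.026 (q = 20%) and 0.040 (q = 30%), against 0.056 and 0.088 under the rule. The PR estimate may become smaller and its interval wider.

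### No eligibility criterion asks whether a parent could attend the PR meetings, so foreseeable non-attendance can cost outcome data in the PR arm alone

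*Combined protocol and SAP*

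**What the plan says.** The combined protocol and SAP sets out parent eligibility in its opening section. The parent criteria begin "Eligible parents had to (a) have access to necessary technology (i.e., computer with camera and microphone, high-speed Internet connection, and a mobile device" and end "and (b) speak English". The remaining criteria concern the child. Nothing there refers to time or to scheduled meetings.

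The same section gives the allocation: "Parents were assigned to either the PR or TR condition using block randomization". The text just before Program Descriptions adds: "Parents were notified to which group they were randomly assigned upon completion of T1". It also says that PR parents who came to none of the sessions received neither the T2 nor the T3 survey. There is no matching rule for TR.

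Under Practiced Routines, parent educators ran "three weekly online meetings", each lasting 1.5 to 2 hours and mostly near the upper end. Availability appears only here: "When participants were assigned to PR, they were grouped based on their availability and assigned to one of five parent educators". Groups averaged 3.7 parents, with a range of 1 to 5. Under Teaching Routines, parents work through the material on their own, without meetings.

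Data Analysis compares the arms by ANCOVA adjusted for the baseline score. It states no analysis set and no method for missing outcomes.

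**The concern.** The two programs make different demands on a parent's time, and the eligibility list does not screen for the heavier one. Whether a parent has any evening or daytime slot free for a weekly meeting can be asked before randomisation. If it is not asked, the answer comes out afterwards, and it matters in one arm only.

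Under the survey rule, a PR parent who attends nothing has no T2 or T3 data. The equivalent TR parent stays in the comparison. Parents with no free time may plausibly differ in stress or family quality of life, and both are outcomes here. Baseline-adjusted ANCOVA removes only the part of such a difference that the baseline score carries.

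The plan already screens both arms for equipment whose described use is in PR: webcam and audio for the video meetings, and a mobile device for the meditation app. Screening everyone for PR's equipment but not for its time demand is inconsistent.

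**Working it through.** The plan gives no sample size, attrition figure, SD or effect size, so there is no figure to reproduce. The check is a reading of the text, followed by an illustration on assumed values.

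**Step 1. Follow one parent with no workable meeting time through the plan.**

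| Stage | If assigned to TR | If assigned to PR |
|---|---|---|
| Eligibility (opening section) | Meets all criteria | Meets all criteria |
| Told of assignment | After T1 | After T1 |
| Program | Can complete it all | Has the online course; attends no meeting |
| T2 and T3 | Sent | Not sent |
| ANCOVA at posttest and follow-up | Can contribute | No outcome to contribute |

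The arms differ only from the program stage onward, after randomisation. The loss therefore arises in PR alone.

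**Step 2. Size of the shift (all inputs assumed).** Let d be the share of randomised PR parents lost for this reason. Let g be the difference in mean outcome, in SD units, between PR attenders and those lost. The mean of all randomised PR parents equals the attenders' mean minus d × g, so analysing attenders alone shifts the PR mean by d × g.

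| d | g = 0.3 | g = 0.5 |
|---|---|---|
| 0.10 | 0.03 | 0.05 |
| 0.20 | 0.06 | 0.10 |
| 0.30 | 0.09 | 0.15 |

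To the extent that the baseline score predicts the difference, ANCOVA would reduce these shifts.

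**Step 3. What such a shift does to a test.** Assume n randomised per arm, SD 1, no true effect, a two-sided nominal level of 0.05 and a normal approximation. The standard error is sqrt(1/(n(1-d)) + 1/n).

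- n = 50, d = 0.10, g = 0.3: SE = sqrt(1/45 + 1/50) = 0.205; shift/SE = 0.03/0.205 = 0.15; type I error 0.052.
- n = 50, d = 0.30, g = 0.5: SE = sqrt(1/35 + 1/50) = 0.220; shift/SE = 0.15/0.220 = 0.68; type I error 0.105.
- n = 100, the same two corners: 0.055 and 0.161.

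At the low end the effect is negligible. At the high end it is not.

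**The case against.** Several points on the other side have force.

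- **The timing of collection is not stated.** A reader might infer that availability was gathered only after assignment. The text says how availability was used in PR, not when it was asked. Consent preceded assignment, and the consent pages are not in the public copy, so the meeting commitment may have been discussed there. What stands is that no stated criterion depends on it.
- **The grouping is itself a mitigation.** Groups were built around parents' availability, across five educators, and could be as small as one. This lowers the number who could find no time, but does not guarantee that it is zero.
- **The reason for non-attendance is not given.** A reader might take the survey rule as evidence that scheduling kept parents away. Loss of interest, family crisis or technical failure would fit equally well.
- **Sample inflation.** It is tempting to argue that non-attenders dilute the contrast and multiply the required sample by 1/(1-q)², that is 1.23 for q = 0.1 and 2.04 for q = 0.3. That applies only if non-attenders are surveyed and gain nothing from PR. Under the current rule they are not surveyed, and PR's videos, forms and meditation app remain open to them.
- **Randomising everyone is legitimate.** Analysed as assigned with full follow-up, it estimates the effect of offering each program, and restricting entry answers a narrower question. This is a fair defence of broad eligibility, but the plan does not follow everyone, so it does not deliver that estimate either.

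**Conclusion.** The point holds as a cheap improvement to the design. The eligibility list leaves out the one PR requirement that TR parents never face, and the survey rule turns the resulting non-attendance into missing outcomes in PR only. The size cannot be established from the documents. The shift of 0.03-0.15 SD rests entirely on an assumed 10-30% loss and an assumed 0.3-0.5 SD difference, and its direction is unknown.

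The documents do not support the stronger claim that settling availability beforehand would cure the imbalance whatever the survey rule. Parents who say they are available may still attend nothing, and under the present rule they would still be lost from PR alone. The survey rule is the main source of harm; this point concerns one foreseeable route into it.

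**What to change.** 1. Record every parent's weekly availability at screening or with T1, before assignment.
2. Add one criterion for both arms: the parent could attend the three weekly PR meetings at a workable time if assigned to PR. It should cover all three meetings, so that a parent free for only one does not qualify.
3. Form the PR groups from that record after assignment.
4. Separately, send T2 and T3 to everyone randomised and analyse as assigned. Steps 1 to 3 remove only the non-attendance that can be foreseen at screening.

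The cost is one screening question, one eligibility line and a somewhat narrower population, a restriction of the same kind as the technology criteria. Cost and benefit move together: if 10-30% of parents truly had no workable time, about that share would be excluded. Because the document is written in the past tense, the action for the trial as run is to report how many PR parents attended no session, with reasons where known. The eligibility change would serve any further enrolment or a successor trial.

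### Practiced Routines (PR) is delivered in cohorts under five educators and Teaching Routines (TR) is self-directed, but the stated analysis has no cohort or educator term; if shared delivery makes PR outcomes correlate, the PR-TR and within-PR standard errors are too small

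*Combined protocol and SAP*

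**What the plan says.** **Allocation.** The opening section states that "Parents were assigned to either the PR or TR condition using block randomization". The unit is the individual parent. Block size and allocation ratio are not given.

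**Delivery of PR.** Under Program Descriptions, Practiced Routines, once parents had been allocated to PR "they were grouped based on their availability and assigned to one of five parent educators". They attended three weekly video meetings of 1.5 to 2 hours in "small groups of parents (M = 3.7; range = 1 – 5) per cohort", with brief educator contact before and between meetings.

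**Delivery of TR.** "Teaching Routines was entirely self-directed", with no feedback beyond automated completion responses.

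**Analysis.** The Data Analysis section gives two methods. For change within a program: "Change was evaluated over time within condition using repeated-measures" t-tests. For the comparison of programs: "The ANCOVA models (adjusted for baseline scores) were used for analyses of change in the outcome measures at posttest and follow-up". Neither includes a cohort or educator term. No section mentions a cluster-robust standard error, an ICC or a design effect.

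**The concern.** This is a partially nested design: parents are clustered by delivery in one arm and not in the other. Parents who share up to six hours of live discussion, and an educator, may end with more similar outcomes than parents who do not. If so, the PR arm holds less independent information than its head count suggests. The ordinary ANCOVA and the paired t-test would then give intervals that are too narrow and reject too often.

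Two sets of results are exposed. One is the PR-TR contrast, the only randomised comparison and the one tied to the hypotheses of differential change. The other is the set of within-PR t-tests, which are uncontrolled but serve the stated aim of judging whether each program brought improvement. Because no ICC is planned or reported, a reader cannot tell how large the problem is.

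**Working it through.** **Inputs from the documents.** Mean cohort size 3.7, range 1 to 5; five educators; clustering in PR only; individual randomisation. There is no stated sample size, alpha, ICC or power figure, so there is nothing of the plan's own to reproduce.

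**Assumptions.** Equal arms, equal total variance, two-sided 5%, 3.7 analysed parents in every cohort, and a delivery-induced ICC of 0.01 to 0.20 (of baseline-adjusted outcomes for the ANCOVA, of change scores for the t-test).

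**Formulas.**
- Design effect in PR: DE = 1 + (m − 1) × ICC = 1 + 2.7 × ICC.
- True/naive variance, within-PR t-test: DE.
- True/naive variance, PR-TR: (DE + 1)/2, since only one of two equal arms is clustered.
- True alpha = 2 × [1 − Φ(1.96/√ratio)].

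| ICC | DE | (DE+1)/2 | PR-TR alpha | Within-PR alpha |
|---|---|---|---|---|
| 0.01 | 1.027 | 1.0135 | 5.2% | 5.3% |
| 0.05 | 1.135 | 1.0675 | 5.8% | 6.6% |
| 0.10 | 1.27 | 1.135 | 6.6% | 8.2% |
| 0.20 | 1.54 | 1.27 | 8.2% | 11.4% |

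**Sensitivity to cluster size.**
- *Unequal cohorts.* The relevant size is Σn²/Σn. With assumed sizes 1,2,3,3,3,4,4,4,4,5,5,5,5 this is 196/48 = 4.08. At ICC 0.10, alpha is 6.8% (PR-TR) and 8.7% (within PR). With mean 3.7 and range 1 to 5 it cannot exceed 3.7 + (1.3 × 2.7)/3.7 = 4.65, which gives 7.1% and 9.3%.
- *Survey loss.* With 2.5 to 3 analysed per cohort and ICC 0.05, (DE + 1)/2 = 1.0375 to 1.05, so PR-TR alpha is 5.4 to 5.6%.
- *Educator level.* Parents per educator are not given. Assuming 6 to 15 and an educator ICC of 0.05, DE = 1 + 5 × 0.05 = 1.25 to 1 + 14 × 0.05 = 1.70. Alpha is then 6.5 to 9.2% (PR-TR) and 8.0 to 13.3% (within PR). These exceed the cohort figures at the same ICC because each educator covers more parents.

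**Check by simulation** (assumed 48 per arm, the 13 cohorts above, baseline correlation 0.6, 20,000 replicates). At delivery ICC 0/0.05/0.10/0.20 the ANCOVA rejects 5.0/6.1/7.1/8.9% of the time and the within-PR t-test 5.0/7.1/8.9/12.2%.

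**Which correlation counts.** Cohorts were formed after allocation. If similar parents were merely placed together and the meetings added nothing shared, the grouping only labels parents already randomised and does not change the variance of the PR mean. In the same layout, sorting on an availability score that explains 5/10/20% of variance gives 5.1/5.2/5.2% for the ANCOVA and 4.8/4.9/5.1% for the t-test, so there is no inflation.

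**The case against.** **The effect may be small.** There were only three meetings, some cohorts held one parent, session guides were used, and content fidelity averaged 99%. At ICC 0.01 to 0.05 the PR-TR error is 5.2 to 5.8%; the 8 to 11% figures need an ICC of 0.10 to 0.20 and mostly concern the uncontrolled within-PR tests. This stands. It limits the size of the point but does not remove it: participation fidelity ranged from 53 to 100%, and only 34% of sessions were checked.

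**The model fitted may differ from the text.** The opening section calls the design mixed-model, and Data Analysis is brief. The label describes the design, and no random effect for cohort or educator follows. The omission from the text is certain; that the fitted models assumed independence is inferred.

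**The 3.7 may not be the analysed size.** It describes meeting groups. Survey loss would reduce it; if it is average attendance, the cohorts were larger. The direction is uncertain.

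**The remedy gains little at low ICC.** In a simulation of the within-PR model with an unbounded cohort variance, alpha at ICC 0.01 was 6.1% adjusted against 5.7% unadjusted; at 0.05 it was 5.8% against 6.8%. This also stands.

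**Stronger readings a reader might infer.** One is that the reported error rates are known to be inflated; without an ICC, this cannot be said. Another is that any similarity within cohorts proves inflation; similarity due only to availability does not. A third is that all within-program tests are affected; those in TR are not.

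**Conclusion.** The concern holds in conditional form. The documents describe clustering by delivery in PR alone and an analysis that, as written, ignores it. The PR-TR and within-PR standard errors are too small to the extent that shared meetings or educators induce correlation. Under the assumptions above, cohort-level inflation is slight to moderate for PR-TR and larger within PR; educator-level correlation would add to it. The size in this trial is unknown, because every magnitude rests on an assumed ICC, equal arms and an assumed analysed cohort size. This should be corrected because the remedy is cheap. It is not evidence that the findings are wrong.

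**What to change.** **Between programs.** At posttest and at follow-up, fit a partially nested mixed model: baseline score and program as fixed effects, a random cohort intercept in PR only (each TR parent a cluster of one), arm-specific residual variances, and Satterthwaite or Kenward-Roger degrees of freedom. Keep the cohort term whatever its estimate. State whether its variance may go below zero: in simulation a zero bound made the PR-TR test conservative at low ICC (3.7% at ICC 0, against 5.2% unbounded), while an unbounded variance makes some intervals narrower than the unadjusted ones.

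**Within PR.** Replace the t-test with an intercept-only model of change carrying the same cohort term. Keep the t-test for TR.

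**Reporting.** Give the cohort ICC for each outcome with its imprecision. With 13 cohorts the SD of one estimate is about 0.13 to 0.14, so a single value says little.

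**Educator.** Add a sensitivity analysis with an educator random effect in PR. State that five educators leave only about 4 degrees of freedom and that the cohort model does not fully correct educator-level correlation.

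**Cost.** A re-analysis and revised wording, with no new data collection. Cohort identifiers are needed, and the documents do not confirm that they were stored. Since "Participants who did not attend any PR sessions were not sent T2 or T3", analysed PR parents should each have a cohort. At ICC 0.05 to 0.20, intervals widen by √1.0675 to √1.27, about 3 to 13%, for PR-TR and by √1.135 to √1.54, about 7 to 24%, within PR, before lost degrees of freedom. If the correlation is only sorting, the adjusted tests are somewhat conservative.
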